5. TRIAL TREATMENT

No IMP will be administered in this trial.

5.1 Concomitant Medications and Therapies

Only immunosuppressive medications will be recorded in the concomitant medication module in the eCRF throughout the trial, beginning from screening to end of trial. Medication and therapies to treat recurrent AMR episodes will be recorded in the eCRF.

Recorded information will include indication, name of drug, route of administration and start and stop date.

6. TRIAL PROCEDURES

6.1 Trial Visits

The flow chart of all trial visits, including applicable visit windows, is provided in Section 6.2. A list of scheduled activities/assessments for each visit is provided in Sections 6.1.1 to 6.1.2 and further details of how each activity/assessment is to be performed is given in the subsections to Section 7.

All subjects considered for the trial must be informed about the trial, verbally and in writing, and give their written consent before any trial procedure is performed.

Informed consent may be signed at the last visit in the feeder trial. For each subject, the duration of the trial, including the time from signing informed consent to end of trial will not exceed 3 years and 10 months. This includes 6 months if informed consent is signed at the end of trial in feeder trial and the visit window of 4 months at Year 3 visit.

If a subject is not able to attend a planned visit, the subject may be contacted by phone and assessments described in this protocol may be collected from a local laboratory.

6.1.1 Screening

Screening may be conducted at the earliest at the last visit in feeder trial and at the latest at Year 1 (one year after start of treatment in feeder trial +/- the visit window of 2 months).

The following assessments and activities will be performed:

- Check inclusion and exclusion criteria
- Sign informed consent, see section 15.5
- Assessment of graft survival. For subjects with graft loss after last visit in the feeder trial, date, reason for graft loss, medical history, and root cause will be recorded.
- Record patient survival (if applicable, date and cause of death)

6.1.2 Year 1, Year 2, and Year 3 (End-of-Trial)

The following visit windows applies:

Year 1: (+/- 2 months)

Year 2 and Year 3 (End-of-Trial): (+/- 4 months)

The following activities and assessments will be performed:

- Assessment of graft survival. For subjects with graft loss since last visit in the feeder trial or screening (if screening is done at a separate visit), date, reason for graft loss, medical history, and root cause will be recorded.
- Record patient survival (if applicable, date and cause of death)
- Collect information about graft rejection episodes, (classified by Banff 2017 or later). For-cause biopsies together with contemporaneous local DSA analyses, kidney function parameters (P-creatinine, U-albumin/creatinine ratio) and treatments (e.g. plasma exchange and IVIg) will be collected to assess the rejection episodes.
- Record information from standard of care biopsies, if available
- Sample for S/P-creatinine will be drawn (eGFR will be calculated by the Sponsor)
- Collect urine sample for measurement of albumin/creatinine ratio
- Sample for HLA antibodies, including DSA, and ADA will be drawn
- Record comorbidity such as infections, malignancy, diabetes mellitus, cardiovascular events and comorbidity leading to worsening of kidney function, that occurred after end of trial in feeder trial
- Record current immunosuppressive medications
- Record treatment with dialysis
- AEs related to trial procedure or IMP in feeder trial will be recorded, see section 9

6.2 Flow Chart

Table 2. Flow chart.

| Visit (post treatment in feeder trial) | Screening | Year 1 | Year 2 | Year 3 (EOT) |
|---|-----------------------------------|---------------------|---------------------|---------------------|
| Visit window | EOT feeder trial to Year 1 | +/- 2 months | +/- 4 months | +/- 4 months |
| Assessment | | | | |
| Informed consent | x ¹ | | | |
| Inclusion and exclusion criteria | x ¹ | | | |
| Enrolment and allocation of subject no | x ¹ | | | |
| Graft survival status | x | x | x | x |
| Patient survival status | x | x | x | x |
| Graft rejection episodes ² | | x | x | x |
| Kidney graft biopsy reports ³ | | x | x | x |
| S/P-creatinine, eGFR calculation (performed by Sponsor) | | x | x | x |
| U-Albumin/creatinine ratio | | x | x | x |
| Sample for HLA antibodies, including DSA, and ADA central lab | | x | x | x |
| Comorbidity ⁴ | | x | x | x |
| Current immunosuppressive medication | | x | x | x |
| Treatment with dialysis | | x | x | x |
| Adverse events related to trial procedure or IMP in feeder trial ⁵ | | x | x | x |

Footnote

- ¹⁾ Signing of Informed consent and check of inclusion and exclusion criteria can be done any time between end of the feeder trial and at Year 1.
- ²⁾ Record graft rejection episodes (classified by the Banff 2017 or later version), creatinine and DSAs taken in standard of care due to the episode and treatments (e.g. plasma exchange and IVIg).
- ³⁾ If standard of care kidney biopsies are collected for any reason, at any time-point, e.g. suspected graft rejections, record information in the eCRF.
- ⁴⁾ Record comorbidity that are medically relevant and registered in the subject's medical record. Medically relevant comorbidity are infections, malignancy, diabetes mellitus, cardiovascular events and comorbidity leading to worsening of kidney function
- ⁵⁾ Only Adverse events caused by a procedure in the protocol (e.g. blood sampling) or related to IMP in feeder trial will be recorded.

7. TRIAL ASSESSMENTS

7.1 Assessments related to Primary Endpoint

The primary endpoint of this trial is to determine the overall graft survival, defined as time from start of treatment (imlifidase or plasma exchange) of active or chronic active AMR in feeder trial to graft loss, evaluated at year 3. Graft loss is defined as permanent return to dialysis for at least 6 weeks, re-transplantation, or nephrectomy. The date of graft loss will be recorded. If dialysis is used to define graft loss, the date of graft loss is the first day of the dialysis period defining the graft loss.

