7.2.2 Patient survival

Overall patient survival is defined as time from start of treatment (imlifidase or plasma exchange) of active or chronic active AMR in the feeder trial to death for any cause, evaluated at Year 3. The date and cause of death will be recorded.

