12.3.1 Primary efficacy analysis

Overall graft survival at Year 3. Graft survival is defined as time from start of treatment (imlifidase or plasma exchange) of active or chronic active AMR in feeder trial to graft loss, evaluated at year 3. Graft loss is defined as permanent return to dialysis for at least 6 weeks, re-transplantation, or nephrectomy. If dialysis is used to define graft loss, the date of graft loss will be the first day of the last ongoing dialysis period reported.

The primary endpoint will be analysed by the Kaplan-Meier survival method. The overall graft survival will be tabulated and presented graphically with 95% confidence limits by treatment.

The following events will be censored at the time of occurrence: withdrawal from the trial without graft loss, evaluation time point and end of trial without graft loss.

The reason for graft loss will be tabulated by time.

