9.1 Tables

Table 14.1.1 Patient disposition, including reason for discontinuation (All screened patients).

Table 14.1.2 Protocol Deviations (FAS).

Table 14.1.3 Demography and body measurements (FAS).

Table 14.1.4 Medical and surgical history (FAS).

Table 14.1.5 Concomitant medication (FAS).

Table 14.1.6 Previous transplant kidney history (FAS).

Table 14.2.1 MFI levels for DSA – by time point (FAS).

Table 14.2.2 Kidney function (based on S/P-creatinine analysis) (FAS).

Table 14.2.3 Proportion of patients with absence of graft loss at 1 year, 2 years and 3 years (FAS)

Table 14.2.4 Proportions of patients with presumed or biopsy proven AMR episodes (FAS).

Table 14.2.5 Proportion of patients with presumed or biopsy-proven rejection episodes, (other than AMR episodes) (FAS).

Table 14.2.6 Total IgG – by timepoint (FAS).

Table 14.2.7 Proportion of patients having reduction in total IgG (FAS).

Table 14.2.8. Patient survival (FAS)

Table 14.3.1 Overview of AEs (FAS).

Table 14.3.2 Summary of AEs – by SOC and PT (FAS).

Table 14.3.3 Summary of AEs – by causality (FAS).

Table 14.3.4 Summary of AEs – by severity (FAS).

Table 14.3.6 Summary of SAEs (FAS).

Table 14.3.7 Summary of SAEs – by causality (FAS).

Table 14.3.10 Summary of SAEs leading to death (FAS).

Table 14.3.11 Summary of SAEs leading to withdrawal (FAS).

Table 14.4.1 Summary of clinical chemistry variables (U-Albumin, Creatinine, U-Albumin/creatinine ratio) – by time point (FAS).

Table 14.4.2 Anti imlifidase IgG (ADA) (mg/mL) – by time point (FAS)

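### Under the written definition, a subject who dies within six weeks of returning to dialysis for graft failure is not a graft-loss event, and neither document says how that death enters the graft-survival analysis

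*Protocol*

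**What the plan says.** The event definition is the same in Protocol 7.1, Protocol 12.3.1 and SAP 4.4.1: "Graft loss is defined as permanent return to dialysis for at least 6 weeks, re-transplantation, or nephrectomy". Death is not one of the three routes.

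Protocol 7.1 adds a dating rule for losses that qualify through dialysis: "the date of graft loss is the first day of the dialysis period defining the graft loss". Protocol 12.3.1 and SAP 4.4.1 word the dating differently, but there too it applies only once dialysis has been used to establish the loss.

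On the analysis, Protocol 12.3.1 says: "The primary endpoint will be analysed by the Kaplan-Meier survival method". The observations to be censored are "withdrawal from the trial without graft loss, evaluation time point and end of trial without graft loss", and SAP 4.4.1 repeats that list. Death is named neither as an event nor as a reason for censoring. SAP 9.1 also plans Table 14.2.3, "Proportion of patients with absence of graft loss at 1 year, 2 years and 3 years (FAS", without saying how deaths enter it.

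Death is captured separately as the secondary endpoint of patient survival. Protocol 7.2.2 states: "The date and cause of death will be recorded". At the yearly visits, Protocol 6.1.2 asks sites to "Record treatment with dialysis". The reason for and root cause of graft loss are requested there only for subjects who have had a graft loss.

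**The concern.** The six-week minimum plausibly serves to keep temporary dialysis out of the event count. It also excludes a different kind of case: the graft has failed, dialysis has started for that reason, and the subject dies before the six weeks are up. Unless the subject has already been re-transplanted or had the graft removed, no later status check can turn this into an event.

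Graft survival is the primary endpoint, and the omitted failure is tied to death. If the subject is censored, the censoring is informative: the Kaplan-Meier estimate treats the subject as having the same prospects as those still at risk, although the graft had already failed. The error goes in one direction only, towards higher graft survival, in whichever arm has the case. The arms are expected to hold about 20 and 10 subjects, so a single case would be visible in the result.

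**Working it through.** The documents state no event rate, power or sample-size figure on this point, so there is nothing to reproduce. The check has two parts.

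**1. Does any clause cover the case?** Take a subject who dies in week 4 of dialysis started for graft failure.

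- Dialysis route: not met, because four weeks is less than six.
- Re-transplantation or nephrectomy: not met, by assumption.
- Dating rules: they date a loss that has already qualified and do not create one.
- Censoring list: it covers withdrawal, the evaluation time point and end of trial. Death is absent.
- Patient survival: it records the death but does not return the graft failure to the primary endpoint.

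So the case is a non-event, and how it then enters the analysis is not specified.

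**2. How much does one case move the estimate?**

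Inputs from the documents: about 20 imlifidase and 10 plasma exchange subjects (Protocol 12.6), analysed by Kaplan-Meier (Protocol 12.3.1).

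Assumptions: one such subject, with dialysis start and death both placed at month 12; b = 0 to 3 other graft losses at months 24, 28 and 32; everyone else followed to month 36.

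With n in the arm and the b other losses all later than the death, Year 3 survival is:

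- censored at death: (n − 1 − b)/(n − 1)
- kept as free of graft loss to Year 3: (n − b)/n
- counted as a loss at dialysis start: (n − 1 − b)/n

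For n = 10 and b = 2 these are 7/9 = 77.8%, 8/10 = 80.0% and 7/10 = 70.0%.

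| n | Other losses | Censored | Kept as loss-free | Counted as loss | Censored minus counted |
|---|---|---|---|---|---|
| 10 | 0 | 100% | 100% | 90.0% | 10.0 points |
| 10 | 1 | 88.9% | 90.0% | 80.0% | 8.9 points |
| 10 | 2 | 77.8% | 80.0% | 70.0% | 7.8 points |
| 10 | 3 | 66.7% | 70.0% | 60.0% | 6.7 points |
| 20 | 0 | 100% | 100% | 95.0% | 5.0 points |
| 20 | 1 | 94.7% | 95.0% | 90.0% | 4.7 points |
| 20 | 2 | 89.5% | 90.0% | 85.0% | 4.5 points |
| 20 | 3 | 84.2% | 85.0% | 80.0% | 4.2 points |

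If the subject is kept as loss-free, the gap from counting a loss is always 1/n: 10 points for n = 10 and 5 points for n = 20. That is what could happen in Table 14.2.3 if deaths stay in both numerator and denominator. Under censoring the gap is (n − 1 − b)/[n(n − 1)], which reaches 1/n when no loss follows the death.

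**The case against.** A reader might infer that the plan counts fatal graft failures as surviving grafts. The documents do not say that. Death is simply absent from the censoring list. The likely default is censoring at death, which takes the subject out of the risk set and does not score a working graft at Year 3. Table 14.2.3 could show such a subject as free of graft loss, but that is not stated either. A reader might also infer that every death after graft failure is missed. That is too broad: a death after six or more weeks of permanent dialysis still leaves a counted loss, as does a prior nephrectomy or re-transplantation.

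Further points on the other side have weight:

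- The number of cases is unknown and may be zero. The analysis is descriptive, with no hypothesis test.
- Death soon after starting dialysis may reflect another illness, so these need not be the most severe graft failures.
- The reason for dialysis is not a specified data item. Reason and root cause are tied to graft loss, which these subjects do not have under the written rule.
- SAP 6 says the study was terminated in January 2023, SAP 10 dates the SAP 12 May 2023, and SAP 2.3 describes an open-label study. Redefining the event now is post hoc, and a protocol amendment cannot change what was collected.

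These points limit the size of the concern and shape the remedy. They do not remove the gap: applied exactly, the rule makes a failed graft a non-event, and no clause corrects it. A rule that censors deaths without graft loss would leave this failure outside the event count as well.

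**Conclusion.** The point holds in a narrow form. A return to dialysis for graft failure that ends in death before six weeks, with no prior re-transplantation or nephrectomy, is not a graft-loss event under the wording used in both documents. Whether the subject is then censored or shown as loss-free, graft survival is biased upward.

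Under the assumed scenarios, with censoring as the probable default, one case is worth about 6.7 to 10 points of Year 3 Kaplan-Meier survival in an arm of 10, and 4.2 to 5 points in an arm of 20. These figures rest on one case per arm, on the assumed event times, and on complete follow-up of everyone else. The documents give no rate, and with no such case the effect is nil.

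**What to change.** Make the change in a SAP revision, or as a documented change to the planned analysis under Protocol 13 and 13.3:

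- For the analysis, count dialysis started for graft failure and still ongoing at death as graft loss whatever its length, dated at the first day of that dialysis period. Do not count dialysis recorded as given for a reversible cause.
- Apply the same rule to Table 14.2.3.
- List the cases. If there are none, one sentence says so.
- Report the Kaplan-Meier estimate under the as-written definition alongside. The study is open-label and has already ended, so readers need to see both.

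The cost is one classification rule, a short listing and one extra Kaplan-Meier run. With at most 30 subjects, checking each death for ongoing dialysis is little work. Dialysis treatment and the date and cause of death are already collected, but the reason for dialysis is not a specified item for these subjects, so the few deaths need a source query. Some classifications will rest on judgement; the second estimate shows how much depends on them.

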7.2 Assessments related to Secondary Endpoints

7.2.1 Overall graft survival at Years 1 and 2

Graft survival at Year 3 is the primary endpoint but graft survival will be evaluated at Years 1 and 2.

7.2.2 Patient survival

Overall patient survival is defined as time from start of treatment (imlifidase or plasma exchange) of active or chronic active AMR in the feeder trial to death for any cause, evaluated at Year 3. The date and cause of death will be recorded.

7.2.3 Kidney function

Evaluation of kidney function will be based on S/P-creatinine analysis and calculation of filtration rate (eGFR) using the MDRD GFR equation. Calculation of eGFR will be done directly in the eCRF. Albumin/creatinine ratio in urine will be collected.

7.2.4 AMR rejection episodes and Graft rejection episodes (other than AMR episodes)

Information about rejection episodes will be collected, according to Banff 2017 or later classification. For-cause biopsies together with contemporaneous local DSA analyses, kidney function parameters (creatinine, albumin/creatinine ratio in urine) and treatments (e.g. plasma exchange and IVIg) will be collected to assess the rejection episodes.

7.2.5 Donor-specific antibody (DSA) levels

Samples for determination of DSA will be analyzed in a single antigen bead assay (SAB-HLA). These assays allow determination of the mean fluorescence intensity (MFI) of antibodies in subject serum reacting to an array of individual HLA immobilized to beads. Analyses of DSA, will be performed centrally at Hansa Biopharma, Lund, Sweden, for samples taken at the visits. The date and actual time of collection of each sample will be recorded in the eCRF.

DSA analysed as standard of care and associated with a graft rejection episode will be recorded in the eCRF. DSAs for each patient will be identified by the respective site.

7.2.6 Immunogenicity by Anti-Drug Antibodies (ADA)

Samples for the determination of ADA levels in serum will be analysed for [REDACTED] [REDACTED]. The analysis will be performed at the central laboratory, [REDACTED] [REDACTED]. Full details of the analytical method used, and the analysis results will be described in a separate bioanalytical report. The ADA sample will be collected at all visits. The date and time of collection will be recorded on the laboratory requisition form and in the eCRF.

7.2.7 Comorbidity

Information about comorbidities that are medically relevant and registered in the subjects' medical record will be collected. Medically relevant comorbidity are infections, malignancy, diabetes mellitus, cardiovascular events and comorbidities leading to worsening of kidney function.

7.2.8 Demographics

Information about gender, race and age (year) will be collected.

8. BIOLOGICAL SAMPLING PROCEDURES

8.1 Volume of Blood

The total blood volume obtained will be about 60 mL over 3 years.

8.2 Handling, Storage and Destruction of Biological Samples

Samples analysed at the local laboratory will be disposed according to local practice.

Biological blood samples collected for central analysis may be stored by the sponsor for a maximum of 5 years after completion of the trial report.

Details on handling of biological samples will be described in the laboratory manual that will be provided to the center prior to inclusion of the first patient.

8.3 Chain of Custody of Biological Samples

A full chain of custody is maintained for all samples throughout their life cycle.

The principal investigator keeps full traceability of collected biological samples from the patients while in storage at the centre until shipment and keeps documentation of receipt of arrival.

The sample receiver keeps full traceability of the samples while in storage and during use until used or disposed.

Hansa Biopharma keeps oversight of the entire life cycle through internal procedures, monitoring of trial sites and auditing of external laboratory providers.

8.4 Withdrawal of Informed Consent for Biological Samples

If a subject withdraws consent to the use of biological samples, the samples will be disposed/destroyed, if not already analysed and documented.

The principal investigator:

- Will ensure that subject withdrawal of informed consent is notified immediately to Hansa Biopharma.
- Will ensure that biological samples from that subject, if stored at the trial site, are immediately identified, disposed/destructed and the action documented.
- Will ensure the local laboratory(ies) holding the samples is/are informed about the withdrawn consent immediately and that samples are disposed/destructed, and the action documented returned to the trial site.

Hansa Biopharma ensures the central laboratory(ies) holding the samples is/are informed about the withdrawn consent immediately and that samples are disposed/destructed, and the action documented returned to the trial site.

In the event that analysis/research has already been performed, Hansa Biopharma will retain the results and associated data for regulatory reasons, but these will not be used in any subsequent analyses.

9. ADVERSE EVENTS AND SERIOUS ADVERSE EVENTS

9.1 Definitions

9.1.1 Adverse Event

An adverse event (AE) is the development of an undesirable medical condition or the deterioration of a pre-existing medical condition following or during exposure to a pharmaceutical product or trial procedure.

No IMP will be administered in this trial and only AEs that the investigator judges as related to IMP administered in the feeder trial, and adverse events caused by a procedure in the protocol (such as blood sampling) will be captured and reported in this trial.

9.1.2 Serious Adverse Event

A serious adverse event (SAE) is an AE or suspected adverse reaction (SAR) that is considered "serious" if, in the view of either the investigator or Hansa Biopharma, it results in any of the following outcomes:

- Results in death
- Is immediately life-threatening
- Requires in-patient hospitalisation or prolongation of existing hospitalisation
- Results in persistent or significant disability or incapacity
- Is a congenital abnormality or birth defect
- Is an important medical event that may jeopardise the subject or may require medical intervention to prevent one of the outcomes listed above. Examples of such events include allergic bronchospasm requiring intensive treatment in an emergency room or at home, blood dyscrasias or convulsions that do not result in inpatient hospitalization, or the development of drug dependency or drug abuse.

Life-threatening event: An adverse event or suspected adverse reaction is considered "life-threatening" if, in the view of either the investigator or Hansa Biopharma, its occurrence places the patient or subject at immediate risk of death. It does not include an adverse event or suspected adverse reaction that, had it occurred in a more severe form, might have caused death.

Disability is defined as a substantial disruption in a person's ability to conduct normal life functions.

Hospitalisation: Admittance to an emergency room for observation without being admitted to the hospital may be considered to be an AE but is not considered as an SAE. However, complications that occur during hospitalization are AEs, and if a complication prolongs hospitalization, the event is considered serious.

